### 5.5.6 Rescue medication

Not applicable.

### 5.5.7 Concomitant treatment

All on-going concomitant medications taken at the time of the Baseline visit and during the study must be recorded. In addition, any medications that may have been taken during any gap between the completion of the prior study and enrollment into this extension study should also be recorded, even if the medication is not ongoing at the time of enrollment. Medications that were recorded during the previous study and had a recorded end prior to completion of the previous study do not need to be re-recorded in this study. Both the start date and the end date for each medication should be captured on the “the “Concomitant Medications/Significant Non-Drug Therapies eCRF or Steroid treatment of MS relapses eCRF, as applicable. Use of the following treatments is allowed to manage potential adverse reactions associated with the study drug:

- anticholinergics (atropine s.c. or i.v.) for treatment of symptomatic bradycardia as the first line treatment, up to 3 mg/day;
- beta-agonists/sympathomimetics (dopamine drip 5-20µg/kg/min or epinephrine drip 2-10 µg/min) for treatment of non-responsive bradycardia.

For more recommendations for management of bradycardia, refer to [Appendix 4](#).

A standard short course of intravenous corticosteroids (3-5 days of up to 1,000 mg methylprednisolone/day) on an inpatient or outpatient basis is recommended for the treatment of relapses if clinically warranted (standard of care procedures should be followed during treatment) and should be recorded on the Steroid treatment of MS relapses eCRF. Tapering with oral corticosteroids is not recommended.

The investigator should instruct the patient to notify the study site about any new medications he/she takes after the start of the study drug. All medications and significant non-drug therapies (including physical therapy and blood transfusions) administered after the patient starts treatment with study drug must be recorded on the Concomitant medications/Significant Non-Drug Therapies eCRF or Steroid treatment of MS relapses eCRF.

Vaccination may be less effective during and for up to two months after treatment with fingolimod.

### 5.5.8 Prohibited treatment

Use of the following treatments is NOT allowed concomitantly with the study drug during the course of the study:

- Immunosuppressive medication (e.g. cyclosporine, azathioprine, methotrexate, cyclophosphamide, mitoxantrone, cladribine);
- Other concomitant medications: immunoglobulins, monoclonal antibodies, adrenocorticotrophic hormone (ACTH-other than if used as a short course (e.g. less than 1 week) for the treatment of MS relapse);
- Medications used to treat MS, which may include glatiramer acetate (Copaxone®), interferon β-1a i.m. (Avonex®), interferon β-1a s.c. (Rebif®), interferon β-1b

(Betaseron®/Betaferon®), natalizumab (Tysabri®), azathioprine, methotrexate or any other medications used as MS-disease-modifying agents;

- Class Ia (e.g. quinidine, disopyramide) or class III (e.g. amiodarone, sotalol) antiarrhythmics.

The administration of any live or live attenuated vaccine (including for measles) should be avoided while patients are receiving study drug and for 2 months after study drug discontinuation. Following Varicella zoster virus (VZV) vaccination, the initiation of study drug should be postponed by 1 month to allow full effect of vaccination to occur.

### **5.5.9 Discontinuation of study treatment and premature patient withdrawal**

Patients may voluntarily withdraw from the study for any reason at any time. They may be considered withdrawn if they state an intention to withdraw, fail to return for visits, or become lost to follow-up for any other reason.

When a patient withdraws from Study Part One and does not continue on fingolimod, either in a study or non-study setting, they must return for two Follow-up visits, 3 months and 6 months after stopping study drug.

When a patient withdraws from Study Part Two, and does not continue on fingolimod, either in a study or non-study setting, they must return for one Follow-up visit, 3 months after stopping study drug.

If premature withdrawal occurs for any reason, the investigator must make every effort to determine the primary reason for a patient's premature withdrawal from the study and record this information on the appropriate eCRF.

Study drug must be discontinued for a given patient if the investigator determines that continuing it would result in a significant risk for that patient. In addition, study drug must be discontinued based on results of safety monitoring as outlined in [Appendix 5: Guidance on safety monitoring](#) and [Appendix 7: Guidance for Ophthalmic Monitoring](#). The following conditions/events may be considered sufficient to support a decision about the study drug discontinuation in individual cases:

- serious adverse event (e.g. cardiac failure, diagnosed malignancy, new neurological symptoms accompanied by MRI findings unexpected for MS) abnormal laboratory value(s) or abnormal test result(s) (e.g. ophthalmic findings).
- withdrawal of consent
- pregnancy (please see [Section 6.5.8](#) and [Section 7.3](#))
- use of prohibited medications, listed in [Section 4.2](#) and [Section 5.5.8](#).
- adverse events
- protocol deviation
- unsatisfactory therapeutic effect
- patient's condition no longer requires study treatment
- administrative problems (e.g. patient's non-compliance)
- discontinuation warranted as per local label requirements

In addition to scheduled visits, patients who discontinue study drug due to adverse events or abnormalities on safety monitoring tests must be followed up with additional visits as needed in order to confirm the resolution of abnormalities.

Document the date and primary reason for stopping the study drug on the appropriate page of the eCRF. If study medication is restarted as per protocol, the reason for the interruption of treatment and date of interruption should be appropriately documented in the source documents as well as in the Dosage Administration eCRF.

For patients who are lost to follow-up (i.e. those patients whose status is unclear because they fail to appear for study visits without stating an intention to withdraw), the investigator should show "due diligence" by documenting in the source documents steps taken to contact the patient, e.g. dates of telephone calls, registered letters, etc.

If a patient permanently discontinues from study drug, the investigator must also contact the IRT system to register the patient's discontinuation from study drug.

Patients who are prematurely withdrawn from the study will not be replaced by an equal number of newly enrolled patients.

#### **5.5.10 Emergency unblinding of treatment assignment**

Not applicable as this is an open-label study.

#### **5.5.11 Study completion and post-study treatment**

Study Part One completion is planned for 30 Jun 2016. Individual patient's end of treatment visits should occur at their routine 6 monthly scheduled visit closest to 30 June 2016 to ensure all patients complete within the window for the end of Study Part One.

The end of the study (completion of Study Part Two) is planned for 30 June 2018. Individual patient's end of treatment visits should occur at their routine 6 monthly scheduled visit closest to 30 June 2018 to ensure all patients complete within the window for the end of the study.

The investigator must provide follow-up medical care for all patients who are prematurely discontinued from the study, or must refer them back to their referring physician for appropriate care.

#### **5.5.12 Early study termination**

The study can be terminated at any time for any reason by Novartis. Should this be necessary, the patient should be seen as soon as possible and treated as described in [Section 5.5.9](#) for a prematurely withdrawn patient. The investigator may be informed of additional procedures to be followed in order to ensure that adequate consideration is given to the protection of the patient's interests. The investigator will be responsible for informing IRBs and/or ECs of the early termination of the trial.

## **6 Visit schedule and assessments**

[Table 6-1](#) and [6-2](#) list all assessments, and indicates with an "X" the visits when they are performed and recorded in the clinical database, with an "S" indicates when a performed

[figure not shown]
assessment is to be recorded on source documentation, and an “S1” indicates that source documentation should be present to confirm the procedure was performed as part of the previous fingolimod trial (Specific to the Baseline visit only). If an “S1” procedure was not performed in the previous trial, it has to be performed at Baseline. Assessments performed at the final visit of the previous fingolimod trial can fulfill the requirements of the Baseline only if they are completed within 14 days of enrollment in CFTY720D2399.

Patients should follow as much as possible the visit schedule with an allowed “visit window” of  $\pm 5$  days for bi-weekly visits, of  $\pm 10$  days for monthly visits, of  $\pm 14$  days for quarterly visits and of  $\pm 30$  days for bi-annual visits. If a visit was performed outside the visit window, any subsequent visits should be performed according to the original visit schedule. In the study, one month is defined as 30 calendar days.

[figure not shown]
Upon availability of the locally approved prescribing information, completion of any additional assessments required by the local label becomes the responsibility of the investigator. The assessments should be completed for all patients, unless prohibited by local regulations. Any findings qualifying as AEs/SAEs should be reported as such.

**Table 6-1 Assessment schedule (Study Part One)**

Visit No.*	Base line V1	V112 	V2	V3	V4	V5	V6	V7...	Study Completion or Premature Dis-continuation*	FU 1 	FU 2 
Study month	Day 1	Month 1	Month 3	Month 6	Month 9	Month 12	Month 18	Every 6 Months until SC			
Informed consent	XS										
Demography	S1										
Inclusion/exclusion criteria	XS										
Previous Study Details	XS										
Amendment 4 Details	Record when Amendment 4 is approved or at Baseline if newly enrolled under Amendment 4										
Amendment 8 Details	Record the signature date of the Amendment 8 patients informed consent										
Medical history	S1										
Concomitant meds	XS	XS	XS	XS	XS	XS	XS	XS	XS	XS	XS
Pregnancy test 	S1	XS	XS	XS	XS	XS	XS	XS	XS	XS	XS
Physical/neuro logical exam	S1		S	S	S	S	S	S	S	S	S
MRI 	XS 2a								XS		

Visit No.*	Base line V1	V112 	V2	V3	V4	V5	V6	V7...	Study Completion or Premature Dis-continuation*	FU 1 	FU 2 	
Study month	Day 1	Month 1	Month 3	Month 6	Month 9	Month 12	Month 18	Every 6 Months until SC				
Skin exam by a qualified physician 	Record as needed											
Eye Exam 	S1		XS	XS					XS			
OCT/Ophthalmic Exam			XS 5a	XS 5a	Record as needed							
PFTs 	Record as needed											
Vital signs	S1	XS	XS	XS	XS	XS	XS	XS	XS	XS	XS	
Screening for hepatitis A, B, C & E and uncontrolled diabetes	XS											
Hematology/	S1	XS	XS	XS	XS	XS	XS	XS	XS	XS	XS	
Blood Chemistry	S1	XS	XS	XS	XS	XS		1/year	XS	XS	XS	
Serology 	XS											
Dispense study drug	S		S	S	S	S	S	S				
Collect unused study drug			S	S	S	S	S	S	S			
First dose monitoring 	XS	Record as needed										
First Dose ECG 	S1	Record as needed										
Dosage Administration Record	XS		XS	XS	XS	XS	XS	XS	XS			
EDSS 	S1			XS		XS	XS	XS	XS	XS	XS	
MSFC 	S1			XS		XS	XS	XS	XS	XS	XS	

Visit No.*	Base line V1	V112 	V2	V3	V4	V5	V6	V7...	Study Completion or Premature Dis-continuation*	FU 1 	FU 2 
Study month	Day 1	Month 1	Month 3	Month 6	Month 9	Month 12	Month 18	Every 6 Months until SC			
MS relapse	XS	XS	XS	XS	XS	XS	XS	XS	XS	XS	XS
Steroid Use	XS	XS	XS	XS	XS	XS	XS	XS	XS	XS	XS
Adverse events/ SAEs	XS	XS	XS	XS	XS	XS	XS	XS	XS	XS	XS
Study Completion									XS		

1. Visit 112 is only applicable for those patients rolling into this trial from any blinded study which has comparator treatment arms (placebo, or active comparator, e.g. study CFTY720D2309) or for any patient who has been off fingolimod treatment for 90 days or greater. All other patients will enroll at Baseline-V1 and come in 3 months later for V2.
 
2. MRIs are required only for patients from phase II/III trials who had MRI assessments in prior FTY trials. Such patients will have the first MRI at V5. If a patient has already had V5 by the time Amendment 4 is approved, the patient should have an unscheduled MRI upon the approval of Amendment 4. Post-Amendment 8 approvals, only the Study Completion MRI is required.
 
2a. Phase II/III patients that enroll /re-enroll into this study under Amendment 8 must have an MRI at the Baseline-V1 visit for new patients or at the re-enrollment visit for re-enrolled patients.
 
3. Pulmonary function testing (FEV1, FVC, DLCO) will be performed if clinically indicated.
 
4. A qualified physician includes either a dermatologist or a physician who has participated in a licensed training program. Record if performed.
 
5. An eye exam will be performed by the treating physician.
 
5a. A 3-month and 6-month OCT scan and ophthalmic exam will be done by an ophthalmologist on any patient who is rolling into this trial from any blinded study which has comparator treatment arms (placebo or active comparator, e.g. study CFTY720D2309) or for any patient who has been off fingolimod treatment for 90 days or greater. Then, to be recorded if performed.
 
6. Serology testing (if not already performed in the previous fingolimod study) will be performed at the Baseline-V1 visit to measure Varicella-zoster virus IgG antibodies.
 
7. Patients enrolling directly from a blinded study may require blinded first-dose observation. First-dose monitoring to be done on any patient who is rolling into this trial from any blinded study which has comparator treatment arms (placebo or active comparator, e.g. study CFTY720D2309) or enrolling from the comparator arm of an open-label controlled study or for any patient who has been off fingolimod treatment for the durations outlined in Appendix 4.
 
8. First dose 12 lead ECGs (pre- and 6 hours post-dose) to be obtained only for those patients rolling into this trial from any blinded study which has comparator treatment arms (placebo) or for any patient who re-initiates fingolimod after having been off fingolimod treatment for the durations outlined in Appendix 4..
 
9. The MSFC will only be done in patients who had previous MSFC assessments in their previous fingolimod study.
											

Visit No.*	Base line V1	V112 	V2	V3	V4	V5	V6	V7...	Study Completion or Premature Dis-continuation*	FU 1 	FU 2 
Study month	Day 1	Month 1	Month 3	Month 6	Month 9	Month 12	Month 18	Every 6 Months until SC			

12. For patients who previously participated in phase II/III trials only (CFTY720D2201/E1, CFTY720D2301/E1, CFTY720D2302/E1, CFTY720D2309/E1, etc), EDSS will be assessed by a certified treating Physician (all phase II/III investigators and any new raters who join during the study will be required to provide one-time proof of Neurostatus EDSS certification). Physicians assessing EDSS for patients from phase IIIb trials do not have to be certified, and individual functional scores are not required.
 
14. Follow up visits (FU) should be scheduled 3 months and 6 months (+/- 14 days) after the last dose of study medication. The follow-up visits should be done only on patients who have stopped the study but do not continue onto fingolimod, either in a study or non-study setting.
 
15. Serum pregnancy tests are collected at visits where chemistry is collected. At other visits, urine pregnancy tests will be performed on-site with kits provided by the central lab.
 
* At each visit the patient must be reminded of the importance of remaining vigilant for infections and, in women of child-bearing age, practicing contraception per protocol.
 
** The Study Completion (SC) assessments to be performed if a patient has prematurely discontinued or if completed the study per protocol. For active patients, Study Completion assessments will be performed when the patient reaches 60 months participation in this study. For patients who have passed the 60 month milestone at the time of Amendment 10 approval at their study site must conduct their Study Completion visit at the next 6-monthly timepoint, or 30-Jun-2016, whichever comes first.
											

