## 3 Investigational plan

### 3.1 Study design

This study uses an open-label, multi-center, single treatment arm design allowing patients participating in the fingolimod multiple sclerosis clinical development program to enroll in order to collect additional long-term safety, tolerability, efficacy, and health outcomes data.

This study has two parts:

[figure not shown]
- Part One, collecting long-term safety, tolerability, efficacy, and health outcomes data through approximately 30-Jun-2016, and
- Part Two\*, collecting limited safety data until approximately 30-Jun-2018, in a subset of patients participating in Part One, and other eligible patients from ongoing fingolimod trials (e.g., CFTY720D2312).

\*Eligibility for Part Two is defined as prior fingolimod study patients who are unable to obtain fingolimod outside a clinical trial.

By June 2016, investigators must determine commercial Gilenya eligibility for all active study patients (i.e., reimbursed for commercial Gilenya). Patients able to obtain commercial Gilenya will then have their End of Study (Part One) visit and exit the study, regardless of their post-study treatment decision (i.e., continuing on Gilenya commercially or transitioning to another treatment option). Patients discontinuing or completing the study at Part One who do not continue on commercial Gilenya must return for two follow-up study visits, 3-months and 6-months post-last dose of fingolimod. Patients who choose to continue on commercial Gilenya outside the study are exempted from the follow-up visits.

Patients not eligible for reimbursed, commercial Gilenya will be offered continued study participation in Part Two until their scheduled study visit closest to 30-Jun-2018 (+/- 30 day visit window), with a reduced assessment schedule (see Table 6-2), for the purpose of collecting additional long-term safety and tolerability data in support of the primary study objective. Patients discontinuing or completing the study after entering Part Two who do not continue on commercial Gilenya must return for one follow-up study visit, 3-months post-last dose of fingolimod. Patients who choose to continue on commercial Gilenya outside the study are exempted from the follow-up visit.

Patients enrolling in either part of the study from blinded studies will remain blinded to the identity of the treatment in the previous study. In order to maintain the blind, the monitoring

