### **Guidance on monitoring of patients with notable lymphopenia**

Fingolimod results in sequestration of a proportion of the circulating lymphocytes in lymph nodes with resultant reduction in circulating lymphocyte counts. Average circulating lymphocyte counts are expected to be around  $0.5-0.6 \times 10^9/L$  or  $500-600$  cells/ $\text{mm}^3$ . As such, the absolute total WBC, neutrophil and lymphocyte counts will be measured at each visit  $y$ . If the absolute lymphocyte count drops below  $0.2 \times 10^9/L$  or  $200$  cells/ $\text{mm}^3$  lymphocyte counts should be repeated regularly, at least monthly, and the patient should be reminded of the risk of infections and instructed to promptly report any symptoms of infections to the investigator. If monthly site visits create a logistical burden for the patient, local lymphocyte testing can be performed, with an eCRF comment added that lymphocyte counts were obtained locally and reviewed by the investigator. Study drug should be temporarily interrupted at the discretion of the investigator. Recovery of lymphocyte counts is expected to take approximately 1-2 months after stopping study drug given the long half-life of fingolimod. The patient should be evaluated and monitored for infections on a regular basis during this period.

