8.1.3 Time in study

For the analysis of ARR from first dose of fingolimod to end of study treatment, the time in study (days) is calculated as: last dose date of fingolimod – first dose date of fingolimod among all studies + 1 day. Similarly, the time in study from first dose of fingolimod among all studies to end of follow-up is calculated as: last available visit/evaluation date across all panels – first dose date of fingolimod among all studies + 1 day.

For the analysis of ARR from first dose of fingolimod among all studies to end of a particular month (i.e. “Month 6”, “Month 12”, “Month 24”, and every 12 months from then on), “Month 0 to X” time in study will be calculated as minimum of (first dose date of fingolimod + integerpart(X/12*365.25) where X denotes the month, last available visit/evaluation date across all panels) – first dose date of fingolimod + 1 day.

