8.1.4 MS relapses analyses

MS relapses analyses will be conducted on the fingolimod full analysis set. All analyses will be done for all relapses (confirmed and unconfirmed) and for confirmed relapses.

A summary of ARRs will be presented by time period (cumulative time intervals: ‘Month 0 to Month 6’, ‘Month 0 to Month 12’, ‘Month 0 to Month 24’, ‘Month 0 to Month 36’, ... incremented by 1 year for each successive interval, plus ‘Month 0 to end of study treatment’ and ‘Month 0 to end of follow-up’) from first dose of fingolimod among all studies. The summary will include number of patients summarized, number of relapses, time in study (days), and group level ARR. In addition, model based estimates of ARR and corresponding two-sided 95% confidence interval will be obtained by fitting a negative binomial regression model adjusted for the number of relapses in the last two years prior to

enrolment in the core study and EDSS score at first dose of fingolimod baseline, with the logarithm of the time in study as the offset variable.

A summary of relapse characteristics will be displayed by time period (consecutive yearly intervals: 'Month 0 to Month 12', 'Month 12 to Month 24', etc., plus 'End of study treatment to End of follow-up') from first dose of fingolimod among all studies. Relapse characteristics will be summarized at a patient level (the number and percent of patients with at least one relapse type) and at a relapse event level (the number and percent of a particular type of relapse out of the total number of relapses). The types of relapses being summarized include: relapses which affect daily activities, relapses which require steroids, and relapses which require hospitalization.

The time to first onset of relapse from first dose date of fingolimod among all studies will be analysed. Specifically, the number of patients at risk, the cumulative number of patients with relapse, the Kaplan-Meier (KM) estimate of the percent of patients without relapse and corresponding standard error and two-sided 95% CI will be provided at each yearly time point (1 year = 360 days). Patients with no relapse, patients for whom follow-up ends before a confirmed relapse occurs, and patients who drop out prior to the relapse will all be censored, i.e. the time to event for these patients will be the time in study (from first dose of fingolimod among all studies to last available visit/evaluation date across all panels).

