8.3.2 EDSS score of 4/6/7 or greater

The time to first EDSS score of 4/6/7 or greater from first dose of fingolimod among all studies will be analysed for patients with a baseline EDSS score of less than X, where X=4, 6, or 7 depending on the analysis being conducted. Specifically, the number of patients at risk, the cumulative number of patients with event, the Kaplan-Meier (KM) estimate of the percent of patients without event and corresponding standard error and two-sided 95% CI will be provided at each yearly time point (1 year = 360 days).

A Kaplan-Meier plot of 3 Kaplan-Meier curves showing time to first EDSS score of X or greater from first dose of fingolimod to the end of the long-term follow-up study Part will be provided, where X is 4, 6, and 7.

The time to event/censoring for Kaplan-Meier analyses will be calculated as follows:

For patients with EDSS score of 4/6/7 or greater:

Time to event = first assessment date (after first dose date of fingolimod among all studies) that patient has an EDSS score of X or greater – first dose date of fingolimod among all studies +1 day.

For patients who do not have EDSS score of 4/6/7 or greater (in other words, censored):

Time to censoring = last EDSS assessment date – first dose date of fingolimod +1 day. If the patient does not have post-baseline EDSS assessment, then that patient will be censored at Day 1 (Time to censoring =1).

A patient will be censored if the patient exits the study without receiving an EDSS score of 4/6/7 or greater after first dose of fingolimod among all studies.

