- The average scores from the 4 trials on the 9-Hole Peg Test (9HPT). The 2 trials for each hand are averaged, converted to the reciprocals of the mean times for each hand and then the 2 reciprocals are averaged, i.e.

$$9HPT_z = (9HPT_{\text{mean}} - 9HPT_{\text{baseline-mean}}) / 9HPT_{\text{baseline-stdev}}$$

- The number of correct answers from the PASAT 3, i.e.

[figure not shown]
$$PASAT3_z = (PASAT3_{\text{mean}} - PASAT3_{\text{baseline-mean}}) / PASAT3_{\text{baseline-stdev}}$$

[figure not shown]
Finally, these individual z-scores are averaged to create an overall composite score:

[figure not shown]
$$MSFC_z = \frac{1}{3} \{9HPT_z - T25FW_z + PASAT3_z\}$$

[figure not shown]
[figure not shown]
The negative value of the T25FT z-score is taken to make the direction of change the same as the other components. In computing $MSFC_z$ for each patient, if any of the individual scores ($9HPT_z$, $T25FW_z$, or $PASAT3_z$) are missing, then $MSFC_z$ will be missing as well.

[figure not shown]
Descriptive statistics on baseline, post-baseline, and change from baseline will be presented for $MSFC_z$ and each subscale score by visit for the fingolimod full analysis set.

9 Safety evaluation

The primary objective of this study is to evaluate the long-term safety and tolerability of fingolimod 0.5 mg in patients with relapsing forms of MS.

Long-term safety will be assessed in terms of adverse events (AEs), laboratory, vital signs (including dose administration monitoring), electrocardiograms (ECG) dose administration monitoring, ophthalmic assessments, pulmonary function tests, and skin assessments. Except for summaries specifically for follow-up (e.g. summaries of Month 3 and Month 6 follow-up visits), serious adverse events, or adverse events after last dose date of fingolimod until end of follow-up, post-baseline safety summaries (not including listings) will limit reporting to only include assessments with dates from first dose date of fingolimod among all studies to last dose date of fingolimod + 45 days.

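### Three long-term efficacy analyses run past the last fingolimod dose, and only patients who stop the drug contribute that off-drug time

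*Protocol*

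**What the plan says.** **Who is followed off drug.** Protocol Table 6-1 schedules relapse and EDSS at FU1 and FU2. Footnote 14 sets the timing, "Follow up visits (FU) should be scheduled 3 months and 6 months (+/- 14 days) after the last dose of study medication", and the population, "The follow-up visits should be done only on patients who have stopped the study but do not continue onto fingolimod". Protocol 3.1 adds: "Patients who choose to continue on commercial Gilenya outside the study are exempted from the follow-up visits". In Part Two there is one such visit, at 3 months, and EDSS is not collected (protocol 3.1, 6.4.2 and Table 6-2).

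**Whether those data are analysed.** SAP Part I section 1 takes in data up to the end of Part I. Section 2.3.1 times the database lock to allow for the 6-month follow-up.

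**How the three analyses end (SAP Part I).**
- Time to first relapse (8.1.4): patients without an event are censored at their time in study, "from first dose of fingolimod among all studies to last available visit/evaluation date across all panels".
- Cumulative ARR (8.1.3): "For the analysis of ARR from first dose of fingolimod among all studies to end of a particular month", time in study stops at the earlier of Month X and the last visit in any panel.
- Time to EDSS 4, 6 or 7 (8.3.2): the event date is the "first assessment date (after first dose date of fingolimod among all studies) that patient has an EDSS score of X or greater". Patients without an event are censored at their last EDSS.

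SAP Part 2, 8.1.3 and 8.1.4, repeats the two relapse rules.

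**Where off-drug time is already kept apart.** The ARR table has one row ending at last dose and a separately labelled row ending at the end of follow-up. Relapse characteristics have their own interval after end of treatment. By-visit EDSS has follow-up windows (2.3.4, Table 4). Section 9 limits most post-baseline safety summaries "to only include assessments with dates from first dose date of fingolimod among all studies to last dose date of fingolimod + 45 days".

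**The concern.** The secondary objective is the long-term efficacy of fingolimod 0.5 mg/day. A patient who continues on commercial drug or enters Part Two leaves the Part I risk set at the last on-study visit. A patient who stops stays in it for up to about six months without treatment. Protocol 5.5.9 lists adverse events and unsatisfactory effect among the reasons for stopping, so the extra time comes from a selected group.

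The resulting curve is neither an on-treatment estimate nor a follow-up of everyone regardless of treatment. Neither Kaplan-Meier analysis has an on-treatment version to set beside it. For the ARR, the later cumulative rows drift towards the end-of-follow-up row without carrying its label.

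**Working it through.** The documents state no rate, event count or power figure on this point, so there is nothing to reproduce. The check has two parts: reading the rules, and an illustration on assumed inputs.

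**1. End dates side by side (SAP Part I)**

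| Analysis | Ends at | Off-drug visits included? |
|---|---|---|
| ARR, Month 0 to end of study treatment | last dose | no |
| ARR, Month 0 to end of follow-up | last visit, any panel | yes, labelled |
| ARR, Month 0 to Month X | earlier of Month X and last visit | yes, not labelled |
| Kaplan-Meier, first relapse | last visit, any panel | yes, not labelled |
| Kaplan-Meier, EDSS 4/6/7 | last EDSS | yes, not labelled |

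**2. Late cumulative ARR rows.** Time is min(first dose + X, last visit) − first dose + 1. Once X exceeds a patient's follow-up, this becomes last visit − first dose + 1, which is the formula of the end-of-follow-up row.

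**3. Visit timing (30-day months, ±14 days).** FU1 falls on days 90 ± 14 = 76 to 104 after last dose, and FU2 on days 180 ± 14 = 166 to 194. A milestone of EDSS 4, 6 or 7 needs one score, so it can be reached at either visit. Six-month confirmed progression (8.3.3) needs at least 166 days between onset and confirmation. FU1 to FU2 spans at most 194 − 76 = 118 days, so an onset at FU1 cannot be confirmed at FU2. With visits in window, FU2 can confirm an off-drug onset only if it falls within 194 − 166 = 28 days of last dose. FU2 can also confirm onsets that occurred on drug.

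**4. ARR illustration.** Assumed: on-drug rate 0.20 per year; T = 5 or 7 years on drug; a share s = 10% to 40% attends 0.5 year of follow-up; off-to-on rate ratio r.

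ARR = 0.20 × (T + 0.5·s·r) / (T + 0.5·s)

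- Off-drug share of person-time: 0.05/7.05 = 0.7% to 0.2/5.2 = 3.8%.
- r = 1: 0.200, no change.
- r = 2: 0.201 to 0.208 (+0.7% to +3.8%).
- r = 4: 0.204 to 0.223 (+2.1% to +11.5%). The top value is 0.20 × (5 + 0.8)/5.2 = 0.223.

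A milder set assumes a mean of 5 years on drug, 15% to 40% stopping, r from 2 to 4, and a raised rate only from month 2, so for 4 of the 6 months. The excess is s × (4/12) × (r − 1) / (T + 0.5·s), from 0.05/5.075 = 1.0% to 0.40/5.2 = 7.7%. Protocol 3.3 projects 7 to 15 years of exposure. At the midpoint of 11 years the same formula gives 0.05/11.075 = 0.5% to 0.40/11.2 = 3.6%.

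**5. Kaplan-Meier illustration (400,000 simulated patients per scenario).** Assumed: on-drug hazard 0.12 per year for first relapse and 0.04 for the milestone; planned end uniform over years 5 to 8; stopping at 5% or 10% per year; all early stoppers and 20% of completers attend 0.5 year of follow-up; off-drug hazard changes at last dose.

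| Event-free at 7.5 years | r | Ends at last dose | Includes follow-up | Fall (points) |
|---|---|---|---|---|
| First relapse, 5%/yr stopping | 2 | 0.406 | 0.390 | 1.6 |
| First relapse, 5%/yr | 4 | 0.408 | 0.365 | 4.3 |
| First relapse, 10%/yr | 2 | 0.407 | 0.384 | 2.3 |
| First relapse, 10%/yr | 4 | 0.405 | 0.342 | 6.3 |
| Milestone, 5%/yr | 2 | 0.742 | 0.733 | 0.9 |
| Milestone, 5%/yr | 4 | 0.742 | 0.714 | 2.8 |
| Milestone, 10%/yr | 2 | 0.742 | 0.727 | 1.5 |
| Milestone, 10%/yr | 4 | 0.743 | 0.700 | 4.3 |

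At r = 1 the two versions agree in every scenario. At 5 years the falls are smaller: 0.8 to 4.1 points for relapse and 0.3 to 2.2 for the milestone. The late tail moves most because continuing patients have left the risk set while stoppers remain in it.

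**The case against.** The best defence is that the SAP never calls these analyses on-treatment. It speaks of time in study and of time from first dose, declares its scope as data to the end of Part I, and in 8.3.3 deliberately counts follow-up visits as scheduled visits. On this view the plan has simply chosen to follow patients beyond treatment. That stands in part: which version should lead is a choice of estimand. It does not explain why only stoppers are followed, or why the off-drug part of the curves goes unmarked.

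Some stronger readings are tempting, and the documents do not support them.
- A reader might infer that the SAP treats all post-treatment relapse and EDSS data as time on fingolimod. It does not: one ARR row ends at last dose, and relapse characteristics and by-visit EDSS separate follow-up.
- A reader might infer from "Recovery of lymphocyte counts is expected to take approximately 1-2 months after stopping study drug given the long half-life of fingolimod" that clinical benefit has gone by FU1. That sentence concerns lymphocyte counts. It gives no time at which protection from relapse or disability ends.
- A reader might infer that safety is cut cleanly at 45 days. Serious adverse events and follow-up summaries are exempt, and the overall notable-abnormality displays include follow-up visits.

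Two further points stand. Censoring at last dose can itself be informative, since patients may stop for lack of effect. Section 8.1.2 also discloses a bias in the opposite direction, because uncounted and off-study time lowers the ARR.

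**Conclusion.** The point holds for the three named Part I analyses and, with one 3-month visit, for the two relapse analyses in Part 2. They include off-drug time contributed only by stoppers, and the two Kaplan-Meier analyses have no version without it. It does not extend to every relapse or EDSS display, and it barely touches confirmed progression (step 3).

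Size and direction cannot be settled from the documents. Every rate, stopping share and exposure length in the illustration is an assumption. The shift is zero if the event rate does not change off drug. If the rate rises, fingolimod looks worse, so a reader should not infer that the rule flatters the drug. On the assumed ratios the effect on the ARR is modest (at most +11.5%, or 0.023 on 0.200), and it reaches a few points in the late Kaplan-Meier tail. The study is single-arm and tests no hypothesis, so no error rate is at stake. This is a worthwhile, inexpensive improvement to interpretability.

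**What to change.** In SAP Part I 8.1.3, 8.1.4 and 8.3.2, and SAP Part 2 8.1.3 and 8.1.4:

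1. Add versions in which both time and events end at the earlier of the last visit and the last fingolimod dose, matching the existing end-of-study-treatment ARR row. Alternatively, prespecify one short lag and apply it to all of them. A lag would keep a completion-visit EDSS dated a few days after last dose. The 45 days used for safety would still exclude an in-window FU1 (day 76 at the earliest), though the documents give no basis for 45 days as an efficacy cut.
2. Label the present versions as including off-drug follow-up.
3. State which version addresses the long-term efficacy objective, and how 8.3.3, where follow-up visits may confirm progression, relates to it.

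The cost is some SAP wording, one extra censoring variable and a few more tables; no new data are needed. The added versions will have slightly fewer events and slightly less person-time, and they carry the risk of informative censoring at last dose. That risk is a reason to show both versions.
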